4.0 SELECTION AND ENROLLMENT OF PARTICIPANTS

4.1 Inclusion Criteria

- 4.1.1 Participant (or legally authorized representative) provides informed consent prior to initiation of any study procedures.
- 4.1.2 Individual ≥18 years of age.
- 4.1.3 Documentation of confirmed active SARS-CoV-2 infection, as determined by a molecular test conducted at any US clinic or laboratory that has a Clinical Laboratory Improvement Amendments (CLIA) certification or its equivalent from any respiratory specimen collected <96 hours **from when the first dose of study treatment is expected to be taken.**
- 4.1.4 Experiencing at least one of the following SARS-CoV-2 infection symptoms **within 24 hours of screening:** fever (can be subjective) OR cough OR shortness of breath.
- 4.1.5 Agrees to not participate in another clinical trial for the treatment of COVID-19 or SARS-CoV-2 during the study period up until reaching hospitalization or 21 days, whichever is earliest.
- 4.1.6 Agrees to not obtain study medications outside of the A5395 study.

4.2 Exclusion Criteria

(Medical history can be by self-report. Refer to the A5395 MOPS.)

- 4.2.1 Need for hospitalization or immediate medical attention in the clinical opinion of the study investigator.
- 4.2.2 History of or current hospitalization for COVID-19.

NOTE: Individuals hospitalized and then discharged, even if only hospitalized for 1 day, are excluded.

4.2.3 History of ventricular arrhythmia or **using antiarrhythmics within the past 30 days**.

4.2.4 Personal or family history of Long QT syndrome.

4.2.5 History of kidney disease.

NOTE A: If the individual responds “yes” but can provide a creatinine clearance (**CrCl**) value **of** ≥ 45 mL/min by Cockcroft-Gault equation **from** within 1 year **of** study entry, the individual may participate.

NOTE B: Please refer to the A5395 PSWP for the website link to the Cockcroft-Gault calculator.

4.2.6 History of ischemic or structural heart disease.

4.2.7 History of hypokalemia or hypomagnesemia or taking potassium supplementation or magnesium supplementation.

4.2.8 Personal medical history of porphyria, retinopathy, severe hepatic impairment, or G6PD deficiency.

4.2.9 Use of drugs with possible anti-SARS-CoV-2 activity within 30 days prior to study entry, e.g., remdesivir, lopinavir/ritonavir fixed dose combination, ribavirin, chloroquine, hydroxychloroquine, and azithromycin, or participation in a clinical trial involving any of these drugs whether for treatment or prophylaxis.

4.2.10 Requirement or expected requirement for a medication that significantly prolongs QT intervals or increases risk for QT prolongation (medications summarized in [section 5.4](#)), from 96 hours prior to study entry through 4 weeks after discontinuation of study treatment **except for escitalopram, citalopram, maprotiline, SC/IM risperidone, carbamazepine, ethosuximine, and zonisamide, which should not be used within 7 days prior to study entry.**

4.2.11 Loop diuretics are exceptions to exclusion criterion 4.2.10 but these cannot be used within 30 days prior to study entry.

4.2.12 Participating in a study where co-enrollment is not allowed.

4.2.13 Receipt of a SARS-CoV-2 vaccination prior to study entry.

4.2.14 Known allergy/sensitivity or any hypersensitivity to components of HCQ, azithromycin, or their formulation.

4.2.15 Active drug or alcohol use or dependence that, in the opinion of the site investigator, would interfere with adherence to study requirements

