HCQ and chloroquine have similar pharmacokinetics, with rapid gastrointestinal absorption and elimination by the kidneys. Both are also metabolized by the cytochrome P450 enzymes (CYP2D6, 2C8, 3A4, and 3A5). HCQ is metabolized to desethylhydroxy-chloroquine, desethylchloroquine, and bidesethylhydroxychloroquine by the liver and excreted by the kidneys, with desethylhydroxychloroquine being most common [17, 18a]. The absorption half-life is 3 to 4 hours and the terminal half-life ranges from 40 to 50 days. Based on modeling of HCQ pharmacokinetics and its antiviral effects, [name] at UCSF found that higher doses of HCQ would be associated with progressive loss of detection

[figure not shown]
[figure not shown]

Figure 2.1-2: *In vitro* Activity of Remdesivir, Hydroxychloroquine, and Chloroquine [10]

of SARS-CoV-2 in the nasopharynx over 6 days of dosing (**Figure 2.1-3**), in a dose-dependent manner [18b]. However, higher doses are also associated with longer QT interval prolongations; thus, **in order to balance the potential risks and benefits for treatment in the outpatient setting**, treatment in this trial will include a loading dose of **800 mg divided into two 400 mg doses taken 12 hours apart starting at enrollment**, followed by 200 mg twice daily for 6 days (12 doses), with a total dose of 3200 mg of HCQ during the study.

HCQ Interactions

HCQ does not have significant interactions with most other medications, but may enhance liver toxicity of select drugs, for example, aurothioglucose, cimetidine, or digoxin. It can also increase the blood plasma concentrations of penicillamine, which may contribute to the development of side effects from penicillamine, and decrease the levels of ampicillin and praziquantel. It can also enhance hypoglycemic effects of insulin and oral hypoglycemic agents.

Azithro Pharmacology

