At Day 20, **for non-sampling subset participants**, an in-person **or remote** visit will occur for assessment of the primary outcome and collection of the Study Diary. At this time the participants are expected to no longer be infectious, if they remain un-hospitalized. For participants that cannot **be reached**, the study staff will contact the alternative contacts the **participant** provided to collect information on these outcome measures. **If the participant is symptomatic on Day 20 and an in-person study visit was planned, the in-person study visit may be delayed (refer to [section 6.2.3](#)) or converted to a remote visit. If a remote Day 20 visit is conducted, arrangements should be made for future transfer of Study Diary from the participant to the study staff (i.e., mailing the Study Diary or sending images) and provision of compensation for study participation.**

At weeks 12 and 24, remote visits will be performed to review longer term disease course. At these visits, study staff will record any hospitalizations or deaths that occurred since the Day 20 visit. Additional approaches (such as querying death registries) may be used as feasible at the sites.

Participants will be instructed to contact study staff immediately if they seek medical help at any time during the study.

Additional Evaluation Subset

Some sites will be selected to conduct more in-person visits, depending on availability of staff, PPE, and isolation rooms.

At pre-selected sites, **at study entry [Day 0] and Days 6 and 20**, a subset of participants who agree will undergo self-collected nasal swabs, staff-collected NP swab,

and blood collection on site under appropriate infection control conditions, as described below. Single sparse pharmacokinetics (PK) sampling will be collected at Days 6 and 20 (refer to [section 11.0](#) for details).

Isolation Procedures

Given that SARS-CoV-2 is spread through respiratory droplets, each site must develop procedures to protect study staff and participants of other trials from infectious exposure. Each site will have a plan for maximal protection by providing PPE, setting up isolation rooms or outside areas, providing special access points or contact with study participants. Each site will develop their own set of procedures for such participant contact.

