6.3.15 Laboratory Evaluations

Laboratory evaluations will be performed on some participants at pre-selected sites. At study entry (Day 0), blood samples should be collected prior to the first dose of study treatment.

Hematology

Per the [SOE](#), participants will have the option to have a blood draw for complete blood cell count (CBC) with automated differential and platelet count. These tests will be performed in real-time at the local clinic laboratory.

Chemistry

Per the [SOE](#), participants will have the option to have a blood draw for liver function tests (ALT, ALP, AST, Total Bilirubin, Direct Bilirubin, and Total Protein) and renal function tests (BUN, Creatinine, Potassium, Glucose, and Sodium). A CrCl will be calculated and recorded by Cockcroft-Gault equation ([see Cockcroft-Gault calculator on the A5395 PSWP](#)). These tests will be performed in real-time at the local clinic laboratory.

Inflammatory Markers

Per the [SOE](#), participants will have the option to have a blood draw for lactate dehydrogenase, C-reactive protein, ferritin and D-dimer. These tests will be performed in real-time at the local clinic laboratory.

Stored Plasma

Per the [SOE](#), blood plasma will be collected and stored for future testing for immune responses and drug levels.

Stored Sera

Per the [SOE](#), blood sera will be collected and stored for future testing for immune responses and to compare antibody levels between treatment and control samples.

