6.3.16 Pharmacokinetics

Per the [SOE](#), single sparse PK sampling will be collected. This will be done on a subset of participants who opt to have their blood drawn. Days 6 and 20 blood collection may be used to measure drug levels to assess drug adherence or surreptitious use of HCQ or Azithro.

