The DSMB will also monitor operational futility. With respect to operational futility, the DSMB may recommend modification or termination of the study if the proportion hospitalized/dying in the control arm is low. In particular, the DSMB might recommend restricting or closing enrollment to the low risk stratum in favor of increasing enrollment to the high-risk stratum. In addition, the DSMB will monitor the loss to follow-up (LTFU) rate. As a benchmark, an overall LTFU rate of more than 10% would be cause for concern. The DSMB should also monitor the treatment cross-over in the placebo arm by participant self-report and, if available, by PK levels of HCQ and Azithro. As a benchmark, a crossover rate of more than 10% in the placebo arm would be a cause for concern.

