11.2 Pharmacology Study Design

11.2.1 Overview

Single sparse sample collected at Days 6 and 20 from a subset of participants will be analyzed using population pharmacokinetic approach using Bayesian methodology, with priors informed by historical controls. The model will be supported by 1) sparse sampling corresponding to Days 6 and 20 trough, collected in subset of participants (n=200); 2) historical data from healthy volunteers and participants treated for COVID 19 in other studies (as Bayesian priors).

Population PK modelling will be used to estimate potential difference in HCQ clearance and exposure in patients treated for COVID-19 from historical

controls. A PK-PD model will be developed to examine the relationship between HCQ and Azithro PK, rate of viral clearance and potential clinical outcomes.

PK analysis may also be undertaken to evaluate whether HCQ and/or Azithro might have been used by participants in the placebo arm.

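### The 30-day exclusion for earlier HCQ is shorter than one stated half-life, and the scheduled Day 6 and Day 20 drug levels do not reliably separate permitted pre-entry use from placebo-arm crossover

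*Protocol*

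**What the plan says.** - **Eligibility.** Protocol 4.2.9 excludes "Use of drugs with possible anti-SARS-CoV-2 activity within 30 days prior to study entry". HCQ and azithromycin are both on its list of examples. The criterion also excludes people who took part in trials of these drugs.
- **Pharmacology.** Section 2.1 states for HCQ: "The absorption half-life is 3 to 4 hours and the terminal half-life ranges from 40 to 50 days". For oral azithromycin it gives 79 hours.
- **Sampling.** Section 3.0 states: "Single sparse pharmacokinetics (PK) sampling will be collected at Days 6 and 20". The Schedule of Evaluations (SOE) agrees, adding a sample at premature study discontinuation. Its PK row has no Day 0 entry.
- **Use of the levels.** Section 6.3.16 says: "Days 6 and 20 blood collection may be used to measure drug levels to assess drug adherence or surreptitious use of HCQ or Azithro". Section 11.2.1 says: "PK analysis may also be undertaken to evaluate whether HCQ and/or Azithro might have been used by participants in the placebo arm".
- **Stored plasma.** Section 6.3.15 says: "blood plasma will be collected and stored for future testing for immune responses and drug levels". The SOE schedules stored plasma at Days 0, 6 and 20, and the Day 0 blood is drawn before the first dose.
- **History.** Table 6.3.5-1 covers all prescription drugs for 7 days, autoimmune prescriptions for 3 months and blinded study treatment for 12 months. No row asks for HCQ or chloroquine by name.
- **Monitoring.** Under 10.5 the DSMB follows placebo-arm crossover by self-report and, where available, PK. "As a benchmark, a crossover rate of more than 10% in the placebo arm would be a cause for concern".

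**The concern.** A drug-level check for crossover has to distinguish two sources of HCQ in a placebo participant: drug taken after entry, which is crossover, and drug taken before entry, which 4.2.9 allows if it ended more than 30 days earlier. With a half-life longer than the exclusion window, the second source can still be present throughout the 21-day primary period.

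If permitted earlier use is counted as crossover, four things are affected:

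- the crossover figure that the DSMB sees, where it rests on PK;
- any crossover sensitivity analysis under 10.6.1;
- adherence readings from the same samples;
- the population PK model of section 11, whose focus is oral clearance. Pre-existing drug in an active-arm participant raises the measured level and, if not modelled, makes clearance look lower than it is.

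**Working it through.** **Inputs.** Window 30 days (4.2.9). HCQ terminal half-life T = 40 to 50 days (2.1). Samples at Days 6 and 20 (3.0, SOE). Subset of 200 participants, so about 100 on placebo under 1:1 allocation. Benchmark 10% (10.5).

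**Context: what the plan says 10% crossover costs.** The control proportion becomes 0.90 × 15% + 0.10 × 10% = 14.5%, as in Table 10.4-2. With 950 per arm (1000 less 5% loss), two-sided 5% and no group-sequential adjustment, power for 14.5% versus 10% is 84.9%, against the 83.6% printed. Without crossover it is 91.0%, against the 90% stated. The plan's figures are reproduced closely. The point here does not depend on them.

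**Step 1: window in half-lives.** 30/50 = 0.60 and 30/40 = 0.75, so less than one half-life.

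**Step 2: residual HCQ.** Fraction of the terminal-phase level left after t days = 2^(-t/T). For a last dose 30 days before entry, the limit of what the window excludes:

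| Time point | t (days) | T = 40 | T = 50 |
|---|---|---|---|
| Day 0 | 30 | 59% | 66% |
| Day 6 | 36 | 54% | 61% |
| Day 20 | 50 | 42% | 50% |

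These are upper limits for eligible participants; earlier stopping leaves less. At 60 days after the last dose 35-44% is left, and at 90 days 21-29%. They are fractions of the terminal-phase level, not of the peak.

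**Step 3: can Days 6 and 20 alone separate the sources?** With no new use, the Day 20 to Day 6 ratio is 2^(-14/T) = 0.78 to 0.82, a fall of 18-22%. A dose taken shortly after entry would decay at the same terminal rate once in that phase, so the slope between the two samples is weak evidence of when the drug was taken.

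**Step 4: what a Day 0 level adds.** For a Day 0 level C0 and no new use, the expected level is C0 × 2^(-6/T) = 0.90 to 0.92 of C0 at Day 6, and C0 × 2^(-20/T) = 0.71 to 0.76 of C0 at Day 20. Detection after an undetectable Day 0 sample, or a level clearly above this decay, points to use after entry.

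**Step 5: what the history catches.** The 3-month autoimmune row and the 12-month blinded-treatment row flag some earlier users, and the trial-participation limb of 4.2.9 removes others. Two groups are missed: off-trial, non-autoimmune use that ended more than 30 days before entry, which lies outside the 7-day prescription row; and off-trial use for any indication that ended more than 3 months before.

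**Step 6: size against the benchmark.** In the subset, one misclassified placebo participant adds 1/100 = 1 percentage point. The documents give no share of prior users. If 2-5% of placebo participants in the subset carried detectable HCQ from before entry (an assumption), apparent crossover would rise by 2-5 points; if none did, it would not change. For scale, an observed 10/100 has a Wilson 95% interval of 5.5% to 17.4%.

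**Azithromycin.** 30 × 24/79 = 9.1 half-lives, so the same difficulty does not arise.

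**The case against.** The strongest reply is that a baseline level can be obtained within the existing text: Day 0 plasma is drawn before dosing, stored, and held partly for drug-level testing. That is correct. A reader might infer that no baseline exists and that the two sources can never be told apart; the documents do not support this. What stands is narrower: neither 6.3.16 nor 11.2 commits to a Day 0 assay or ties it to the crossover question. An assay left to an unspecified later date would also not serve a DSMB planned to review weekly from about 500 participants onward.

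A reader might also infer that every placebo detection will be counted as surreptitious use. No passage says so. Both 6.3.16 and 11.2.1 are permissive, and a classification rule could sit in an analysis plan that is not at hand. But such a plan cannot recover a medication history that was never requested.

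The consequences are also modest. PK feeds the DSMB only where available, the 10% figure is a benchmark and not a stopping rule, and the crossover sensitivity analysis is optional. If the benchmark is read over the whole placebo arm of about 1000, one case moves it by only 0.1 point. It would go too far to say that the primary result is at risk: the modified intention-to-treat comparison does not use crossover status, and prior use is a pre-randomisation characteristic that is balanced in expectation.

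Finally, 4.2.9 sets one window for dissimilar drugs and does not claim to clear HCQ. A window shorter than a half-life is a design choice, not in itself an error. It matters here because the later samples are meant to help detect undisclosed use.

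**Conclusion.** The point holds as a limited, inexpensive improvement. On the protocol's own figures the window is 0.60 to 0.75 of a half-life, and 42-50% of the terminal-phase level can remain at Day 20. The only samples named for detecting undisclosed use do not reliably separate that residue from new use. The reach is the optional PK check in about 100 placebo participants, the DSMB benchmark where PK informs it, a possible sensitivity analysis, and the PK model. The primary analysis is not affected.

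The conclusion assumes first-order terminal decay at the stated half-life and an assay sensitive enough to detect the residue. Section 11.2.4 describes the assays as still in development, and no detection limit is given. The number of participants concerned is unknown, so the size of any inflation in crossover cannot be fixed from the documents, and the bias in clearance is not quantified.

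**What to change.** 1. In the SOE, 6.3.16 and 11.2, commit to assaying HCQ and azithromycin in the stored pre-dose Day 0 plasma of the subset, in time for DSMB reviews that use PK.
2. Count a placebo sample as HCQ crossover only if drug is detected after an undetectable Day 0 sample, or if the level clearly exceeds the expected decay (about 0.90-0.92 of the Day 0 level at Day 6 and 0.71-0.76 at Day 20). Set the margin in advance from assay precision.
3. Enter the Day 0 level as the initial condition in the PK model.
4. Add one line to Table 6.3.5-1 recording any HCQ or chloroquine use in the previous 12 months.
5. The sponsor should reconcile the 30-day window in 4.2.9 with the half-life in 2.1. No washout period is proposed here.

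Cost: about 200 extra assays on plasma already stored and one form line, with no additional visit or blood draw.

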Given that the proposed study will exclude those taking **concomitant** medications with high risk of prolonging QT ([section 5.4.1](#)), we do not feel that electrocardiograms (EKGs) at study entry or during treatment are needed. **We believe that** exclusions on the basis of baseline QTc are unlikely to add significantly to **overall safety, above and beyond the planned exclusion** of participants with higher risk for drug-induced ventricular arrhythmias and cardiac events **based upon** relevant personal or family cardiac history, high risk clinical history including severe renal and liver disease, and those who are taking additional QTc prolonging agents. Further, in the midst of a global pandemic, the risk-benefit assessment must consider a wide range of participants, study staff and resource utilization-related issues. In this case, the condition of TdP is expected to be very rare and the performance of EKGs would require the use of personal protective equipment (PPE), for which supplies must be carefully preserved as the current pandemic escalates, and the risk of additional direct contact between staff and highly infectious study participants. As a result, we feel that the potential benefit of HCQ plus Azithro treatment for a disease with an overall case fatality rate of up to 3% (and based on preliminary estimates in the US, 3-11% among persons aged 65-84 years) outweighs the very small risk of a treatment-related cardiac AE, and therefore do not feel that EKGs at study screening or during treatment would be justified [50, 51].

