The use of mobile devices that can perform ECG and measure vital signs has been discussed extensively by the study team and team leads have discussed the capabilities of select devices with their manufacturers or researchers who have used them. Based on these discussions, we have chosen to not include such monitoring for safety purposes for several reasons. Foremost, real-time monitoring for the large number of participants who will be enrolled at any one time will likely be unmanageable, and our older participants may have a harder time with such devices. Therefore, such monitoring is unlikely to lead to an immediate intervention. In addition, given the short duration of treatment and the long half-life of HCQ and Azithro, discontinuation of these drugs following detection of QTc prolongation, even if feasible, may have limited impact.

To help mitigate the risk of HCQ and Azithro causing TdP, we have followed the guidance from Simpson et al. [74b], which states, “minimizing exposure/contact: It may be reasonable to forego ECG screening to allow patients to remain in quarantine if no high-risk features exist (history of long QT syndrome, concomitant QT prolonging medications, structural or ischemic heart disease,

history of prolonged QTc on any ECG, history of abnormal renal function and/or electrolytes.” Therefore, we will exclude potential participants with underlying conditions associated with TdP, including: history of ventricular arrhythmia or on antiarrhythmics, personal or family history of long QT syndrome, history of hypomagnesemia or hypokalemia, history of structural or ischemic cardiac disease, use of antiepileptic or loop diuretic drugs, or use of drugs that can also prolong the QT interval. We will also have the close monitoring by the DSMB that can assist in quickly identifying safety issues with HCQ.

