5.4.1 Prohibited Medications

- Non-study HCQ and Azithro
- Cardiac medications
 - Antiarrhythmic drugs: Class Ia (quinidine, procainamide, disopyramide); Class III (dofetilide, ibutilide, sotalol)
 - **Loop diuretics (furosemide, bumetanide, torsemide, ethacrynic acid)**
- Non-cardiac medications
 - Diphenhydramine
 - **Antiepileptic medications (carbamazepine, eslicarbazepine, ethosuximide, felbamate, gabapentin, lamotrigine, levetiracetam, oxcabazepine, phenobarbital, phenytoin, piracetam, pregabalin, Rufinamide, stiripentol, tiagabine, topiramate, sodium valproate, valproic acid, zonisamide)**
 - Antipsychotic and antidepressant agents: Neuroleptic (haloperidol, droperidol, thioridazine, chlorpromazine); Atypical antipsychotics (ziprasidone, risperidone, zimeldine, citalopram); Antidepressants (amitriptyline, desipramine, imipramine, maprotiline, doxepin, fluoxetine, escitalopram, citalopram)
 - Antibiotics: quinolone (levofloxacin, moxifloxacin); Macrolide (erythromycin, clarithromycin)
 - Antimalarials (quinine, halofantrine, **chloroquine**)
 - Antiprotozoal (pentamidine)
 - Antifungal (azole group)
 - Antimotility Agents
 - Methadone

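### Criterion 4.2.11 exempts loop diuretics from the whole of 4.2.10 and restores only a 30-day look-back, so expected need for one no longer excludes at entry

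*Protocol*

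**What the plan says.** Criterion 4.2.10 has two parts. What triggers it is "Requirement or expected requirement for a medication that significantly prolongs QT intervals or increases risk for QT prolongation", and the period it covers is "from 96 hours prior to study entry through 4 weeks after discontinuation of study treatment". It therefore looks back at recent use and forward to expected need. The same sentence makes an exception for seven named drugs, "which should not be used within 7 days prior to study entry".

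Criterion 4.2.11 deals with loop diuretics separately: "Loop diuretics are exceptions to exclusion criterion 4.2.10 but these cannot be used within 30 days prior to study entry". It says nothing about need during treatment or afterwards.

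Section 5.4.1 lists four loop diuretics by name as prohibited and gives no end date for the prohibition. Section 9.1 makes a requirement for a prohibited drug a reason to stop study treatment permanently.

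Section 2.2 names, among the conditions for which candidates will be excluded, "use of antiepileptic or loop diuretic drugs, or use of drugs that can also prolong the QT interval". Section 2.1, having referred to the exclusion of people taking high-risk QT-prolonging drugs, concludes: "we do not feel that electrocardiograms (EKGs) at study entry or during treatment are needed".

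**The concern.** A washout of 30 days instead of 4 signals more caution about loop diuretics. The wording delivers that for past use and removes the caution for foreseeable use. The protocol gives no reason for screening expected need less strictly for these drugs than for the others in 5.4.

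What is at stake is a narrow point of participant safety. With no ECG at entry or on treatment, history and drug screening at entry carry much of the QT risk control. A site that applies 4.2.11 as written may enrol someone it already knows will need a prohibited drug. If the need arises during the course, study treatment must stop. If it arises in the 4 weeks after the course, there is no treatment left to stop. The forward period has a purpose, because section 2.1 says of HCQ that "the terminal half-life ranges from 40 to 50 days". Section 2.2 itself accepts that, given the long half-lives, stopping the drugs once QTc prolongation is found may achieve little.

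**Working it through.** No statistical figure is involved. The check sets out the days each rule covers and then takes a test candidate through the criteria.

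**Inputs.** Day 0 is the day of the first dose (6.2.2), taken here as study entry. HCQ or its placebo ends on Day 6, or on Day 7 for some participants (6.3.10). The general look-back is 96 hours = 4 days, and the forward period is 4 weeks = 28 days after treatment stops (4.2.10). The special look-backs are 7 days (seven named drugs, 4.2.10) and 30 days (loop diuretics, 4.2.11).

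**End of the forward period.** 6 + 28 = Day 34, or 7 + 28 = Day 35.

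| Drug group | Days covered by the entry criteria | Does expected need exclude? |
|---|---|---|
| Other QT-risk drugs in 5.4 | Day -4 to Day 34-35 | Yes |
| Seven named drugs, natural reading of 4.2.10 | Day -7 to Day 34-35 | Yes |
| Loop diuretics, 4.2.11 as written | Day -30 to Day 0 | No |
| Loop diuretics, if only the look-back changed | Day -30 to Day 34-35 | Yes |

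For loop diuretics the look-back gains 30 - 4 = 26 days, and the forward 34 to 35 days drop out.

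**Test candidate.** Suppose that a person has taken no loop diuretic for 31 days, is expected to need one next week, and has no other excluding condition.

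1. 4.2.10 does not apply, because 4.2.11 makes loop diuretics exceptions to it.
2. 4.2.11 asks only about the last 30 days, so it is met.
3. No other criterion in 4.2 asks about expected need for a loop diuretic. The person is eligible.
4. After entry, 5.4.1 prohibits the drug. If it is needed by Day 6 or 7, 9.1 stops study treatment. If it is needed between then and Day 34-35, 9.1 has nothing left to stop.

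**Is the gap filled elsewhere?** Section 5.4 requires an interaction review when a concomitant drug is started, and 6.3.6 requires new QT-risk drugs to be recorded. Both act after enrolment. The schedule in 6.1 has no planned contact between Day 20 and Week 12, so roughly the last 14 to 15 days of the forward period (34 - 20 and 35 - 20) depend on the participant calling in.

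**The case against.** The strongest reply is that 4.2.11 is meant only to lengthen the washout and must be read with the rest of the protocol. Section 5.4.1 prohibits loop diuretics and 9.1 stops treatment if one is required, so an investigator who knows that a candidate will need furosemide has little reason to enrol that candidate. Medication history is taken at screening and again at entry (6.3.5), and 4.2 refers sites to a manual that is not at hand. The candidate must also have no ischemic or structural heart disease, no kidney disease unless a creatinine clearance of at least 45 mL/min is documented, no history of hypokalemia or hypomagnesemia and no supplementation for either, and no severe hepatic impairment (4.2.5 to 4.2.8). Few people fit.

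Most of this stands, and it keeps the point small. It does not close the gap. Sections 5.4.1 and 9.1 are not exclusion criteria, and 9.1 covers only the treatment course, not the 4 weeks after it that 4.2.10 set out to protect.

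Three stronger readings are tempting, and the protocol does not support them:

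- *The seven drugs in 4.2.10 also lose the forward screen.* A strictly literal reading allows this. However, the exception follows directly on a time window and supplies another, so it most naturally replaces the 96-hour look-back with 7 days. The literal reading would drop the expected-need screen for the three antiepileptics given a longer washout and keep it for the other 16 of the 19 in 5.4.1. That is a reason to doubt the reading.
- *4.2.11 contradicts the case for omitting ECGs.* The rationale in 2.1 and 2.2 speaks of people who take or use these drugs, not of expected need. Recent users remain excluded, for longer than under the general rule.
- *The HCQ half-life measures the harm.* It explains why a 4-week look-ahead is sensible. The protocol does not link the drug level remaining after this course to a degree of QT risk.

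**Conclusion.** The point holds for loop diuretics. As written, 4.2.11 removes the expected-need part of 4.2.10 and leaves a look-back of Day -30 to Day 0, while the other QT-risk drugs in 5.4 are screened through about Day 34-35. This is a gap in entry screening, not a lapse in the prohibition: after entry 5.4.1 applies to loop diuretics as to every other listed drug.

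Severity is low. The number of affected candidates cannot be derived from the protocol. That it is very small is a judgement, resting on 4.2.5 to 4.2.8 and on how unusual it is to be free of a loop diuretic for 30 days and yet known to need one within about five weeks. The primary endpoint, power and sample size are untouched. The conclusion assumes that sites apply the criteria as worded and that the manual does not already correct them. It is worth acting on because it is a safety criterion in a trial without ECGs and the correction is one sentence.

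**What to change.** Reword 4.2.11 along these lines: *For loop diuretics, criterion 4.2.10 applies with the 96-hour look-back replaced by 30 days; a requirement expected at any time up to 4 weeks after study treatment ends remains exclusionary.*

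For clarity, add to 4.2.10 that the 7-day period for the seven named drugs replaces only the 96-hour look-back.

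The cost is one reworded sentence and one clarifying clause, with no new data, visits or procedures. The downside is the loss of a very small number of otherwise eligible people.
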